#### **5.2.4.      Electrocardiogram**

##### Recording

Twelve-lead resting ECGs (I, II, III, aVR, aVL, aVF, V1 - V6) will be recorded using a computerised electrocardiograph at the time points given in the [Flow Chart](#). Precise electrode placement will be marked with an indelible mark on the skin to allow reproducible placement throughout the trial.

To achieve a stable heart rate at rest and to assure high quality recordings, the site personnel will be instructed to assure a relaxed and quiet environment, so that all subjects are at complete rest.

All ECGs will be recorded for a 10 sec duration after subjects have rested for at least 5 min in a supine position. ECG recording will always precede all other trial procedures scheduled for the same time (except for blood drawing from an intravenous cannula that is already in place) to avoid compromising ECG quality.

ECGs will be recorded as single ECGs or as triplicate ECGs (i.e. three single ECGs recorded within 180 sec) as indicated in the Flow Chart.

ECGs may be repeated for quality reasons for instance due to alternating current artefacts, muscle movements, or electrode dislocation. For repetition within triplicate ECGs the time window of 180 sec applies as well. The repeat ECGs are assigned to the respective scheduled time point.

Additional (unscheduled) ECGs may be recorded for safety reasons. These ECGs are assigned to the prior scheduled time point in the sponsor's database.

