##### Hepatic injury

A hepatic injury is defined by the following alterations of hepatic laboratory parameters:

- an elevation of AST (aspartate transaminase) and/or ALT (alanine transaminase)  $\geq 3$  folds ULN combined with an elevation of total bilirubin  $\geq 2$  folds ULN measured in the same blood draw sample, or
- Aminotransferase (ALT, and/or AST) elevations  $\geq 10$  folds ULN.

These lab findings constitute a hepatic injury alert and the subjects showing these lab abnormalities need to be followed up according to the “DILI checklist” provided in the ISF. In case of clinical symptoms of hepatic injury (icterus, unexplained encephalopathy, unexplained coagulopathy, right upper quadrant abdominal pain, etc.) without lab results (ALT, AST, total bilirubin) available, the investigator should make sure these parameters are analyzed, if necessary, in an unscheduled blood test. Should the results meet the criteria of hepatic injury alert, the procedures described in the DILI checklist should be followed

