#### **7.3.4. Safety analyses**

Safety will be assessed as defined by the endpoints listed in Section [2.1.2](#) and [2.2.2.1](#) based on the treated set (TS). Safety analyses will be descriptive in nature and will be based on BI standards.

For all analyses the treatment actually administered (= treatment at onset) to the subject will be used (any deviations from the randomised treatment will be discussed in the minutes of the Report Planning Meeting).

Treatments will be compared in a descriptive way. In SRD part, the placebo group in the safety evaluation will consist of all subjects treated with placebo, regardless of the dose group in which they were treated. The test treatment groups will be compared to the placebo group in a descriptive way. In DDI part, the test treatment groups (BI 1323495+itraconazole) will be compared to the reference group (BI 1323495 alone) in a descriptive way. Tabulations of frequencies/proportions will be used for the evaluation of categorical (qualitative) data, and tabulations of descriptive statistics will be used to analyse continuous (quantitative) data.

Measurements (such as ECGs, vital signs, or laboratory parameters) or AEs will be assigned to treatments (see Section [4.1](#)) based on the actual treatment at the planned time of the measurement or on the recorded time of AE onset (concept of treatment-emergent AEs). Therefore, measurements planned or AEs recorded prior to intake of trial medication will be assigned to the screening period, those between the first trial medication intake and end of REP (see Section [1.2.3](#)) will be assigned to the treatment period. Events occurring after the REP but prior to next intake or end of trial termination date will be assigned to 'follow-up'. These assignments including the corresponding time intervals will be defined in detail in the TSAP. Note that AEs occurring after the last per protocol contact but entered before database lock will be reported to Pharmacovigilance only and will not be captured in the trial database.

Additionally, further treatment intervals (called analysing treatments) may be defined in the TSAP in order to provide summary statistics for other than above periods, such as combined treatments, on-treatment totals, or periods without treatment effects (such as screening and post-trial intervals).

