## **7.8.2      Laboratory data**

The analyses of laboratory data will be descriptive in nature and will be based on BI standards "Display and Analysis of Laboratory Data" ([9](#)).

Analyses will be based on normalised values, which means transforming to a standard unit and a standard reference range. The original values will be analysed if the transformation into standard unit is not possible for a parameter.

Descriptive statistics of laboratory values over time and for the difference from baseline (see [Section 6.7](#)) will be provided. Frequency tables of changes between baseline and last value on treatment with respect to the reference range will be presented.

Unscheduled measurements of laboratory data will be assumed to be repeat measurements of the most recent scheduled measurement (e.g. for follow-up or confirmation of a particular value). Therefore, unscheduled measurements will be assigned to the planned time point of the previous scheduled measurement. Descriptive statistics will be calculated by planned time point based on the worst value of the subject at that planned time point (or assigned to that planned time point).

Possibly clinically significant abnormal laboratory values are only those identified either in the Investigator's comments or at the Report Planning Meeting at the latest. It is the Investigator's responsibility to decide whether a lab value is clinically significant abnormal or not. Standard or project-specific rules for flagging clinically significant values in an automated manner will not be applied in this study.

Clinically relevant findings in laboratory data will be reported as baseline conditions (prior to first administration of study treatment) or as AEs (after first administration of study treatment) if judged clinically relevant by the investigator, and will be analysed as such.

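### Unscheduled laboratory and vital-sign values are filed at the previous scheduled time point even across a dose, so some post-dose values are tabulated as pre-dose

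*SAP*

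**What the plan says.** SAP 7.8.2 sets three rules for laboratory summaries.

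- Status: "Unscheduled measurements of laboratory data will be assumed to be repeat measurements of the most recent scheduled measurement".
- Time: "Therefore, unscheduled measurements will be assigned to the planned time point of the previous scheduled measurement".
- Value shown: "Descriptive statistics will be calculated by planned time point based on the worst value of the subject at that planned time point", which includes values assigned to that time point.

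SAP 7.8.3 uses the same assignment for vital signs but shows the last value instead of the worst. SAP 6.1 presents both kinds of table by dose group and study period. The phases it defines are stated for the analysis of AEs.

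Protocol 7.3.4 assigns measurements to treatments "based on the actual treatment at the planned time of the measurement". It adds that "measurements planned or AEs recorded prior to intake of trial medication will be assigned to the screening period". It leaves the detail to the SAP, and SAP 4 declares no departure from the protocol. SAP 6.7 defines baseline as the last measurement before BI 1323495 in each period, without saying whether that means actual or assigned time.

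**The concern.** Treating an unscheduled value as a repeat makes sense when it confirms the sample just before it. It does not when a dose was given between the two, because the second value may then reflect the drug. None of the sections above makes an exception for that case.

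Unscheduled samples are usually taken because something is suspected. For hepatic symptoms without laboratory results, protocol 5.2.6.1.4 says that "the investigator should make sure these parameters are analyzed, if necessary, in an unscheduled blood test". If such a sample falls in the gap before the first scheduled post-dose sample, the by-time table shows the abnormality as present before treatment and shows nothing after it. The distortion runs towards no drug effect. SAP 7.8.2 also rules out automated flagging of clinically significant values, so an excursion that the investigator does not judge relevant is seen only in these tables and in the listings.

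**Working it through.** The plan gives no figure to reproduce. The check applies the SAP rule to the protocol flow charts and Table 5.2.3: 1.

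**Laboratory gaps around the BI 1323495 dose, read by sampling occasion**

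| Part | Last scheduled before dose | First scheduled after dose | Post-dose window carried back |
|---|---|---|---|
| SRD part | Day -1 (-18 h) | 4 h | 0-4 h |
| DDI treatment R | Day -1 (-18 h) | 24 h | 0-24 h |
| DDI treatment T | Day -1 (-24 h, set C) | 23 h | 0-23 h |
| MD part | Day 1 (-1 h, set C) | 2 h (set D) | 0-2 h |

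As a share of the 7-day (168 h) residual effect period after a single dose, this is 4/168 = 2.4% in the SRD part and 24/168 = 14.3% in DDI treatment R.

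In DDI treatment R and in the SRD and MD parts the receiving row is planned before intake, so protocol 7.3.4 places it in the screening period. In DDI treatment T the row precedes BI 1323495 but lies in the itraconazole phase, which SAP Table 6.1: 2 counts as on treatment.

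**If the rule is applied parameter by parameter** (not stated in the SAP)

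- In the MD part, sets C and D cover only enzymes and haematology respectively. The next set B sample is at about 23.5 h, so the chemistry window runs to about 23.5 h.
- In DDI treatment T, set B parameters that are not in set C go back to Day -3.
- Prothrombin time, aPTT and INR are in set A only (Visit 1 and end of trial), so any on-treatment value goes back to screening.

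**Vital signs, from the same flow charts**

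The last pre-dose and first post-dose readings are at -2 h and 4 h in both DDI periods, at -2 h and 20 min in the SRD part, and at -1 h and 1 h in the MD part. The windows are therefore 0-4 h, 0-20 min and 0-1 h.

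**Illustration (assumed record, DDI treatment R)**

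ALT is 20 U/L on Day -1, 70 U/L unscheduled at 12 h, and 30 U/L at 24 h.

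1. The 70 is assigned to Day -1. The worst value there is max(20, 70) = 70, so the Day -1 row shows 70 in place of 20.
2. The highest value in a post-dose row is 30. The rise of 70 - 20 = 50 U/L appears in no row.
3. With 14 subjects, the Day -1 mean rises by 50/14 = 3.6 U/L.
4. The change at 24 h is 30 - 20 = +10 if baseline follows actual time, but 30 - 70 = -40 if it follows assigned time.

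**The case against.** The strongest reply is that this is a display matter with other routes intact. Much of that stands.

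- SAP 7 lists all individual values, and protocol 7.3.4 highlights out-of-range values in the listings. In groups of 3 to 14 subjects on active drug, a reader can find one subject's excursion there.
- A finding judged clinically relevant becomes an AE, placed by its onset time. A hepatic injury alert is an AESI with expedited reporting. The primary endpoint of the SRD and MD parts counts subjects with drug-related AEs and does not use these tables.
- SAP 6.7 most naturally reads as actual time, which would protect baseline. The SAP does not say so.
- The internal laboratory standard and the technical ADS plan cited by the SAP are not available here. Either could hold an exception. If one does, a sentence in the SAP would confirm it.

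Four stronger readings are tempting, and the documents do not support them.

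- *ECG tables are biased too.* Protocol 5.2.4 says of unscheduled ECGs that "These ECGs are assigned to the prior scheduled time point in the sponsor's database". That is a storage rule. SAP 7.8.4 plans no ECG summary table, only reporting of relevant findings as baseline conditions or AEs.
- *The shift table loses the signal.* It compares baseline with the last value on treatment. A value from the first 24 h would normally be superseded by later scheduled samples whatever row it was filed in.
- *Every such value moves to screening.* This is not so in DDI T, as shown above.
- *All on-treatment coagulation values are misfiled.* This depends on a parameter-by-parameter reading that the SAP does not state.

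None of this removes the fault in the by-time tables. Applied as written, the rule gives a wrong row.

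**Conclusion.** The point holds for the descriptive laboratory and vital-sign tables. An unscheduled value taken between the dose and the first scheduled post-dose measurement is shown before the dose, displaces the true pre-dose value (worst value for laboratory, last value for vital signs) and is missing after it. The laboratory windows are 0-4 h (SRD), 0-24 h (DDI R), 0-23 h (DDI T) and 0-2 h (MD), with the longer parameter-by-parameter windows only as a conditional extension.

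The documents give no expected number of unscheduled samples. Few are likely, so the effect is on single subjects, although one subject can move a row in groups this small. A reader might infer that the plan conceals drug effects or undermines the safety conclusions. It does not: listings, AEs, AESIs and the primary endpoint are not directly touched. The conclusion assumes that the SAP text is applied literally and that no unseen standard overrides it.

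**What to change.** Add to SAP 7.8.2 and 7.8.3:

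> An unscheduled value is assigned to the previous scheduled time point only if, by actual date and time, no first dose of trial drug in that period (BI 1323495, placebo or itraconazole) lies between them. Otherwise it is assigned to the on-treatment phase by its actual time, shown in a row labelled *unscheduled, on treatment*, and never used as a pre-dose or baseline value. Scheduled measurements keep the planned-time rule.

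Itraconazole belongs in the condition. In DDI Period 2 it starts at -72 h and the next scheduled laboratory sample is at -24 h, so values from those 48 h would otherwise fall back to the Day -3 row.

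The SAP should also say whether the previous scheduled measurement is determined per sampling occasion or per parameter, since the length of several windows depends on it.

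The cost is a few sentences and one programming condition on measurement and dosing times. No new data, procedures or subjects are needed. The only downside is an occasional extra row in the tables.

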## **7.8.3      Vital signs**

The analyses of vital signs (blood pressure and pulse rate) will be descriptive in nature. Descriptive statistics of vital signs over time and for the difference from baseline (see [Section 6.7](#)) will be provided.

Unscheduled measurements of vital signs will be assigned to planned time points in the same way as described above for laboratory data. However, for vital signs, descriptive statistics

will be calculated by planned time point based on the last value of the subject at that planned time point (or assigned to that planned time point).

Clinically relevant findings in vital signs data will be reported as baseline conditions (prior to first administration of study treatment) or as AEs (after first administration of study treatment) if judged clinically relevant by the investigator, and will be analysed as such.

#### **7.8.4 ECG**

Abnormal findings will be reported as baseline conditions (prior to first study drug administration) or as AEs (from first study drug administration onwards) if judged clinically relevant by the investigator.

#### **7.8.5 Others**

Physical examination findings will be reported as relevant medical history/baseline condition (if a condition already exists before first administration of study treatment) or as AE (if condition emerges after first administration of study treatment) and will be summarized as such. No separate listing or analysis of physical examination findings will be prepared.

## **8. TIMEPOINT OF RELEASE OF TREATMENT INFORMATION**

The treatment information will be loaded into the trial database after completion of enrolment, i.e. the randomization has been completed.

## **11. HISTORY TABLE**

Table 11: 1 History table

Version	Date (DD-MMM- YY)	Author	Sections changed	Brief description of change
1	27-AUG-2021	[REDACTED]	None	This is the final TSAP.
